5.6 Expected duration of trial

We aim to initiate the trial in November 2017 and estimate a total recruitment period of one year to include at least 50 and a maximum of 60 eligible patients in this monocenter trial. Quality of life, biological implant safety will be measured for one year after placement of the HEKcite device.

Parameters related to implant will be assessed at routine follow-up consultation until one year after placement of the HEKcite device.

5. Trial Procedures

6.1 By visit

At the screening visit, the informed consent procedure is started. At all other visits, the standard of care procedures for post transplantation patients will be followed. Next to these standard evaluations, the printed version of the KDQOL is filled in by the patients.

6.2 Laboratory tests

Urinalysis, together with the blood samples for both the PK/PD data and the GFR rate will be tested preoperative to have a reference of respectively concentration of immunosuppressants and kidney function. Thus, the patients will give urine and with the dipstick method, the color and clarity will be assessed. For more specific results, a blood sample will also be drawn from the patient to test for GFR rates. The temperature of the patients will be evaluated using ROMED® thermometer at all visits, in order to evaluate longitudinal the effect of temperature on the sensitivity and efficacy of the HEKcite device.

6. Assessment of efficacy

Blood samples are standard of care assessments to evaluate the concentration of the immunosuppressants. We will compare these results with the information we get from the application that is connected to the HEKcite device.

7. Assessment of Safety

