3.3 Secondary endpoints

- Quality of life
- Urinalysis and GFR determination [Time frame: 24 months]
- Assessment of PK/PD data of immunosuppressants level in plasma [Time frame: 24 months]
- Assessment of influence of outside temperature on sensitivity and efficacy of HEKcite device [Time frame: 24 months]
- Effects of immunosuppression weaning procedure on immunosuppression-related side effects (diabetes, hypertension, nephrotoxicity, hyperlipidemia) [Time frame: 24 months]

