- Urinalysis, GFR determination are the basic parameters to determine renal function. These tests will be evaluated every study visit. Also, PK/PD data of immunosuppressants will be checked with blood samples at every study visit. Furthermore, the temperature will be checked to evaluate the effect of the outside temperature on the vasodilatation and vasoconstriction of the microvessels surrounding the HEKcite device, and thus the sensitivity and efficacy of the HEKcite device will be assessed in these different temperature-related circumstances at every study visit. Measurements of the temperature will be done with the ROMED® thermometer in all cases to avoid intervariability between thermometers.

[figure not shown]

Figure 1: Flowchart routine practice

Abbreviations: ESRD: end-stage renal disease, KDQOL: kidney disease quality of life.

Postoperative complications

Since the choice for kidney transplantation depends largely on the patient condition, it is impossible to set one uniform surgical protocol.

Complications related to the transplantation surgery, the implant placement will be registered in the Case Report Form as serious adverse events (SAE) or adverse events (AE), according to the National Cancer Institute Common Toxicity Criteria for Adverse Events (NCI CTCAE) v4,0 guidelines (available from: http://evs.nci.nih.gov/ftp1/CTCAE/CTCAE_4.03_2010-0614_QuickReference_5x7.pdf) Since all interventions are part of routine practice, registration of (S)AEs in the CRF is considered sufficient, and no notification of SAEs will be made to the ethics committee. An AE is any undesirable experience associated with the medical intervention that results in:

- (1) Patient death;

- (2) Life threatening;
- (3) Requires patients hospitalization or prolonged hospitalization;
- (4) Results in a disability;
- (5) Results in permanent damage;
- (6) Results in congenital anomaly or birth defect.

Biological and mechanical stability of the HEKcite device

Biological and mechanical implant stability is determined through evaluation of the peri-implant infection rate, implant loss at routine consultations and at every study visit. In addition, long-term changes in biological and mechanical stability will also be examined clinically at 6 months after placement of the HEKcite device, and again at annual routine follow-up visits at 12 and 24 months.

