3.6 Trial Flowchart

	Screen visit	Surgery (day0)	Day1	Week 1	Week 6	Month 6 postop	12 months postop	24 months postop
Informed consent	X							
Physical examination	X	X	X	X	X	X	X	X
Transplant surgery		X						

Device implantation surgery		X						
Urinalysis	X	X	X	X	X	X	X	X
Blood samples to determine PK/PD	X (baseline)		X	X	X	X	X	X
GFR determination	X	X	X	X	X	X	X	X
Temperature control (ROMED®)	X (baseline)	X	X	X	X	X	X	X
Peri-implant infection rate			X	X	X	X	X	X

4. Selection and withdrawal of subjects

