5.4 Withdrawal of subjects

Since the study comprises prospective collection of routinely-collected data in a database, no additional patient risk is expected. The in-house designed HEKcite protocol is based on the routinely-applied concept of implant loading, but consist of a custom-developed manufacturing process of the actual device. The anticipated side effects or toxicities are thus associated with the surgical placement of the device. They comprise postoperative complications at the transplantation site and device implant site (wound dehiscence, infection). The surgical techniques have been routinely carried out in transplant patients as standard of care in the University Hospital Leuven, campus Gasthuisberg.

Subjects are withdrawn from the clinical trial when they react allergic to the implantable device, when they suffer (Serious) Adverse Events, in case of poor compliance to the immunosuppressive therapy and in case of graft rejection. If withdrawal of the subject appears after screening but before surgical placement of the HEKcite device, the subject will be replaced. If withdrawal of the subject appears after surgical placement, the subject will also be replaced, but already received data will be used for statistical analysis. As the medical caretakers sees fit, poor compliance will also be a reason for withdrawal. In these cases the subject will be withdrawn and replaced, and the data will be used for statistical analysis.

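### The secondary endpoint concerns outside temperature, but the protocol records only the patient's temperature and schedules no ambient reading

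*Protocol*

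**What the plan says.** Section 3.3 lists among the secondary endpoints: "Assessment of influence of outside temperature on sensitivity and efficacy of HEKcite device [Time frame: 24 months". Section 3.4, under clinical evaluation, gives the reason: "the temperature will be checked to evaluate the effect of the outside temperature on the vasodilatation and vasoconstriction of the microvessels" around the device. It then names the instrument ("Measurements of the temperature will be done with the ROMED® thermometer in all cases to avoid intervariability between thermometers") but does not say whether that thermometer reads the room, the outdoor air or the patient.

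Section 6.2 does say: "The temperature of the patients will be evaluated using ROMED® thermometer at all visits". It ties that reading to the device question: "in order to evaluate longitudinal the effect of temperature on the sensitivity and efficacy of the HEKcite device". No body site is given.

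The flowchart has one matching row, "Temperature control (ROMED", marked at every visit. Section 8.1 lists a baseline temperature among the preoperative patient assessments. No section schedules a reading of room or outdoor temperature.

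**The concern.** The endpoint has an exposure (outside temperature) and a response (how well the device performs). To answer it, the exposure must be known at the time of each device reading. Under section 6.2 the variable collected for this purpose is a property of the patient, and the step from one to the other is neither stated nor measured.

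Two readings of the results would then be unsafe. If device error shows no relation to the recorded temperature, that does not show that the device is insensitive to outside temperature, because outside temperature was not in the analysis. If a relation does appear, it could come from the patient's own state rather than the surroundings. Fever is the obvious candidate in immunosuppressed patients after surgery, but that is inference; the protocol draws no such link.

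This is a fault of data collection in the protocol, not detail left to an analysis plan. An analysis plan can choose the model, but it cannot supply a room temperature that nobody wrote down.

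**Working it through.** The protocol attaches no sample size, power or significance level to this endpoint, so there is no figure to reproduce. The check sets the temperature statements side by side and counts visits.

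**What each place says**
- Section 3.3: exposure is outside temperature; no instrument named.
- Section 3.4: exposure is outside temperature; ROMED thermometer; object of measurement not stated.
- Section 6.2: ROMED thermometer, all visits, purpose is the effect of temperature on the device; object of measurement is the patient; site not stated.
- Flowchart: one ROMED temperature row; object not stated.
- Section 8.1: a baseline temperature, listed with patient examinations.

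Section 3.4 alone is ambiguous. Section 6.2 shares its instrument, its visits and its purpose, and it resolves the ambiguity towards the patient. If ambient temperature was intended throughout, section 6.2 is wrong and still has to be changed.

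**Visit count from the flowchart**
- Temperature row: screening, surgery, day 1, week 1, week 6, and months 6, 12 and 24 = 8 visits.
- Rows for room or outdoor temperature: 0.
- Blood for drug levels: screening, day 1, week 1, week 6, and months 6, 12 and 24 = 7 visits.
- Of these, screening precedes implantation, so visits with a temperature, a reference blood level and the device in place: 7 − 1 = 6 per patient.
- Of those 6, day 1 and week 1 (2 visits) fall in the first postoperative week.

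The flowchart has no row for the device reading itself. The count assumes that the device is read when the blood is drawn, in line with the comparison described under assessment of efficacy.

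**Scale over the trial, at full attendance**
- 40 patients (section 9.1 minimum): 40 × 6 = 240 paired readings.
- 50 patients (section 3.7 minimum): 50 × 6 = 300.
- 60 patients (section 3.7 maximum): 60 × 6 = 360.

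Under each of these enrolment figures, the number of paired readings with a scheduled ambient temperature is 0.

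**The case against.** The strongest objection is that section 6.2 names no body site. The mechanism in section 3.4 is local: microvessels around a device under the skin of the forearm. If the thermometer is meant for the skin near the implant, the reading lies on the path from outside temperature to device performance and is not irrelevant. This stands to the extent that the recorded variable cannot be dismissed as uninformative. It does not remove the mismatch, since skin temperature is still not outside temperature and the protocol does not say that skin is meant.

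Second, outdoor temperature could be looked up later from the visit dates. That also stands: outdoor values are unplanned rather than lost. Room temperature at the reading cannot be recovered in that way.

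Third, the weight is modest. This is one of five secondary endpoints in section 3.3, it is absent from the synopsis endpoints, and the statistics section describes the analysis as mainly descriptive. That is fair and limits the priority, not the validity, of the point.

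A reader might infer that the endpoint is confounded by fever and infection. The documents do not support stating this as fact. Section 5.4 does anticipate infection ("They comprise postoperative complications at the transplantation site and device implant site (wound dehiscence, infection"), but nothing in the protocol links fever to perfusion, drug level or device reading. The same section also withdraws subjects who suffer adverse events, so how far infected patients would contribute to later visits is unknown.

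**Conclusion.** The point holds. Sections 3.3 and 3.4 name one exposure, section 6.2 records another for the same purpose, and the exposure in the endpoint is scheduled at none of the 6 post-implant paired visits. This rests on the wording and the flowchart alone. The only assumption is that device readings coincide with the blood draws, and it affects only the count of paired readings.

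Two stronger conclusions are tempting and go too far. One is that the recorded temperature would hardly vary with the surroundings, so that a null result is certain. That would need figures for the spread of patient and ambient temperature, and a known core site, none of which the protocol gives. The other is that the endpoint is beyond rescue. It is not, because outdoor values can be retrieved and the collection plan is easy to amend.

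The consequence is confined to this secondary endpoint. The primary endpoint and the sample size are unaffected. The change should be made, but the trial's main result does not depend on it.

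**What to change.** Reconcile sections 3.3, 3.4, 6.2 and the flowchart in one of two ways.

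**If outside temperature is the question.** In section 6.2 and the flowchart's temperature row, add room temperature at each post-implant visit with a paired device and blood reading, plus same-day outdoor temperature from a public weather record. State the body site of the patient reading. Relate the device-minus-blood difference to room and outdoor temperature with an analysis that allows for repeated measurements per patient. Report it with and without patient temperature: if that reading is taken on the skin it could be a mediator, and adjusting for it could remove part of the effect sought.

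Two limits should be acknowledged. Clinic room temperature may itself vary little, which is a reason to collect the outdoor value too. For patients still in hospital at the early visits, outdoor temperature may not reflect the conditions at the implant.

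**If patient temperature is the question.** Rename the endpoint in sections 3.3 and 3.4 accordingly, state the site, and draw no conclusion about outside temperature.

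The cost of the first option is one or two extra case report form fields per visit, a room thermometer and a weather lookup, with no added procedure for patients. The second costs only a text amendment, but gives up the question as now posed.

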8.1 Specification, timing and recording of safety parameters

Preoperatively, standard of care will be provided to the subject, in order to determine safety. Patient will be informed about possible hazards. The surgery and extra implantation will once again be explained to ensure complete knowledge for the patient. Physical examination will be performed, together with urinalysis, baseline temperature, and baseline blood tests to determine GFR. These are all noted in the flowchart. During surgery itself, standard of care measurements will be provided and surgeon is allowed to take actions if any adverse reactions occur.

Postoperatively, standard of care measurements will be provided. Also, the patient will stay in the hospital as long as needed, as evaluated by the treating physician. Aside from the standard of care measurements, flow chart will be followed strictly in order to get the least variability in the study.

All adverse reactions are determined and reported to the appropriate regulations. If needed, patients can be excluded from the trial.

8.2 Procedures for recording and reporting adverse events (AE)

8.2.1 Definitions in Law of May 7, 2004 concerning experiments on the human person

Adverse reaction (AR): all untoward and unintended responses to an investigational medicinal product or to an experiment and, when an investigational product is concerned, related to any dose administered;

Adverse event (AE): any untoward medical occurrence in a patient or subject of the treated group during an experiment, and which does not necessarily have a causal relationship with this treatment

Unexpected adverse reaction (UAR): an adverse reaction, the nature or severity of which is not consistent with the information on the experiment, and, when a clinical trial is concerned, with the applicable product information (e.g. investigator's brochure for an unauthorised investigational product or the patient leaflet joined to the summary of product characteristics for an authorised product);

Serious adverse event (SAE) or serious adverse reaction (SAR): any untoward medical occurrence or effect that results in death, is life-threatening, requires hospitalisation or prolongation of existing hospitalisation, results in persistent or significant disability or incapacity, or is a congenital anomaly or birth defect, and this, when it is a clinical trial, at any dose;

Suspected unexpected serious adverse reaction (SUSAR): is an AR that is serious and unexpected (meaning that nature or severity of the AR is not consistent with the Investigational Medicinal Product reference safety information, which is the Investigator's Brochure) and is judged by either the investigator or the sponsor as having a reasonable suspected causal relationship with the investigational medicinal product.

8.2.2 Notification of adverse events

The investigator shall report all serious adverse events immediately, after first knowledge, to the sponsor except for those that the protocol or investigator's brochure identifies as not requiring

immediate reporting. The immediate report shall be followed by detailed, written reports. The immediate and follow-up reports shall identify subjects by code numbers.

Adverse events and/or laboratory abnormalities identified in the protocol as critical to safety evaluations shall be reported to the sponsor according to the reporting requirements and within the terms specified in the protocol

For reported deaths of a subject, the investigator shall supply the sponsor and the accredited ethics committee with any additional information requested.

The sponsor shall keep detailed records of all adverse events which are reported to him by the investigator or investigators. These records shall be submitted to the minister if the experiment is being conducted in Belgium, if he so requests.

8.2.3 Notification of serious adverse reactions

The sponsor shall ensure that all relevant information about suspected unexpected serious adverse reactions that are fatal or life-threatening is recorded and reported as soon as possible to the minister, to the competent authorities in all the Member States concerned in the case of a trial, and to the competent ethics committee, and in any case no later than seven days after knowledge by the sponsor of such a case, and that relevant follow-up information is subsequently communicated within an additional eight days.

All other suspected unexpected serious adverse reactions shall be reported to the minister, to the competent authorities of all Member States concerned in the case of a clinical trial and to the ethics committee concerned as soon as possible but within a maximum of fifteen days of first knowledge by the sponsor.

The sponsor shall also inform the other investigators.

Once a year throughout the experiment, the sponsor shall provide the minister and the ethics committee in Belgium and those of the member States in whose territory the trial is conducted in the case of a multicentre trial, with a listing of all suspected serious adverse reactions which have occurred over this period and a report of the subjects' safety.

Regarding those adverse events and serious adverse reactions the Principal Investigator will take all reasonable measures, in consultation with Sponsor, to protect subjects at risk following the occurrence of such events.

8.2.4 Adverse events that do not require reporting

Define here any AE's or SAE's that are expected and do not require reporting for this trial. For trials where the IMP is licensed, it is permissible to state that events or reactions listed in the SmPC do not need to be reported. Please define the period for AE reporting – eg randomisation, or first dose until 30 days post final IMP administration

8.3 Treatment stopping rules

8.4 Data monitoring committee (DMC)

Some indications for setting up a data monitoring committee:

- Life-threatening disease
- Patient population (e.g. pediatric population)
- Prior knowledge or strong suspicion that a treatment under consideration has the potential to harm patients
- Complex study design

For further information:

http://www.emea.europa.eu/docs/en_GB/document_library/Scientific_guideline/2009/09/WC500003635.pdf

8. Statistics

Wilcoxon-matched pairs test or repeated measures ANOVA will be applied to examine the evolution of QOL, assessed with the kidney disease quality of life (KDQOL), at respectively the two and three time-points for analysis of the primary endpoint hypothesis.

Statistical analysis will primarily consist of descriptive analysis. Wilcoxon-matched pairs test or repeated measures ANOVA will be applied to examine the evolution of different parameters at several time points. Regression analysis will be performed to examine the influence of different variables on biological and mechanical stability. All analysis will be performed using Prism® software (GraphPad Prism 5, Inc., La Jolla, CA) and SPSS software (version 21, IBM SPSS statistics, Chicago, IL).

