Purpose of clinical trial	
The purpose of this study is to assess accuracy and reliability of the HEKcite therapeutic drug monitoring device and compare these results with blood samples acquired at predetermined time points in kidney transplantation patients.
 
To date, only static data via blood samples is available, and too many grafts are rejected because of lack of dynamic measurements. This HEKcite biosensor provides a dynamic measurement device

	
which will improve drug compliance and the knowledge about receptor occupancy of therapeutic drugs in humans, and will eventually lead to fewer graft rejections, and thus better overall survival rates.

Primary objective	
Assessment of the accuracy and reliability of the monitoring device compared to reference standard of care blood values.

Secondary objective (s)	
To evaluate the mechanical stability of the HEKcite device To evaluate the biological stability of the HEKcite device after 6 months To evaluate the impact of the HEKcite device on drug compliance To evaluate the impact of the HEKcite device on graft functionality To evaluate the impact of the HEKcite device on patient' quality of life, assessed through KDQOL To evaluate the impact

Trial Design	
Open-label, interventional trial

Endpoints	
Graft survival [Time frame: 24 months] Urinalysis and GFR determination [Time frame: 24 months] Effects of immunosuppression weaning procedure on immunosuppression-related side effects (diabetes, hypertension, nephrotoxicity, hyperlipidemia) [Time frame: 24 months]

Sample Size	
50

Summary of eligibility criteria	
18 years to 75 years (adult, senior) Both sexes, no healthy volunteers

IMP, dosage and route of administration	Immunosuppressants, normal dosage, standard of care
Active comparator product(s)	None
Maximum duration of treatment of a Subject	24 months
Version and date of final protocol	20/09/2017
Version and date of protocol amendments	x

2. Background and rationale

3. Trial objectives and Design

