3.1 Trial objectives

We aim to demonstrate the added value of the of the HEKcite therapeutic drug monitoring device and compare these results with blood samples acquired at predetermined time points in kidney transplantation patients. Accuracy and reliability of the monitoring device will be assessed by comparison to reference blood values.

Postop quality of life will be assessed using a KDQOL. Patient will fill a pre-printed form with the KDQOL at the day of surgery, and at every study visit. Patients will also reports the time and the dose of analgesics they are taking post operatively to control pain in that form. Patients will submit all the data to the surgeons at all follow-up appointments.

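### The primary objective is device-versus-blood agreement, but the only comparative tests named examine change over time, and repeated-measures ANOVA discards partly observed patients

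*Protocol*

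**What the plan says.** The synopsis gives the primary objective as "Assessment of the accuracy and reliability of the monitoring device compared to reference standard of care blood values". Section 3.1 repeats it: "Accuracy and reliability of the monitoring device will be assessed by comparison to reference blood values". Section 6, Assessment of efficacy, describes blood concentrations as standard of care and adds "We will compare these results with the information we get from the application that is connected to the HEKcite device". It names no statistic and no acceptable error.

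Section 8, Statistics, says the analysis will be mainly descriptive and then names three inferential methods:

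- For change over time: "Wilcoxon-matched pairs test or repeated measures ANOVA will be applied to examine the evolution of different parameters at several time points".
- For KDQOL, the same two tests, "at respectively the two and three time-points for analysis of the primary endpoint hypothesis".
- For implant stability only: "Regression analysis will be performed to examine the influence of different variables on biological and mechanical stability".

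Section 3.2 lists graft survival as the primary endpoint and section 3.3 lists quality of life as secondary. KDQOL collection is set out in section 3.1: "Patient will fill a pre-printed form with the KDQOL at the day of surgery, and at every study visit". Section 5.4 withdraws subjects for allergy to the device, (serious) adverse events, poor compliance or graft rejection, replaces them, and keeps the data of those withdrawn after implantation in the analysis. Section 9.3, where missing-data handling would stand, contains only template guidance.

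**The concern.** Accuracy against a reference is a question of agreement: how far a single device reading may lie from the blood value, and how consistently. Wilcoxon and repeated-measures ANOVA ask whether the typical value shifts between paired or repeated measurements. They are silent on scatter, which decides whether a monitoring device is usable. As section 8 stands, the objective that motivates the trial has no named inferential analysis, while a secondary endpoint carries the primary hypothesis.

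The choice of ANOVA adds a second problem. In its classical form it uses only patients observed at every analysed visit. Section 5.4 removes patients because of adverse events, rejection or poor compliance, so those discarded are the ones who did badly, and the remaining evolution of KDQOL or GFR would describe the uneventful patients.

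**Working it through.** The protocol gives no figure to reproduce here. Its sample sizes (at least 40 in section 9.1, 50 in the synopsis, 50 to 60 in section 3.7) come without alpha, SD or agreement limit. The error sizes, missing rates and two-sided alpha of 0.05 below are therefore assumptions.

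**1. What a paired location test would say about agreement.** Simulated device-minus-blood differences, 4,000 runs per case, one pair per patient. Limits of agreement = bias ± 1.96 × SD of differences.

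| n | Bias | SD of differences | 95% limits | Wilcoxon p < 0.05 |
|---|---|---|---|---|
| 50 | 0 | 10% of reference | ±20% | 5.1% |
| 50 | 0 | 30% | ±59% | 5.1% |
| 50 | 0 | 50% | ±98% | 5.4% |
| 50 | 5% | 5% | −5% to +15% | 100% |

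With no bias the rejection rate stays at the nominal 5% however wide the scatter. A second simulation, in units of the between-patient SD of blood values, gave the same pattern at n = 40, 50 and 60:

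- No bias, error SD 2: limits about ±3.9, concordance about 0.32, flagged in 5% to 6% of runs.
- Bias 0.05, error SD 0.08: concordance 0.995, flagged in 97% to over 99%.

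The paired t-test, which equals a two-level repeated-measures ANOVA, behaved the same way.

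**2. Complete-case loss in repeated-measures ANOVA.** With an independent chance m of missing each of k analysed visits, expected completers = 50 × (1 − m)^k.

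| m | k = 3 (KDQOL as section 8 plans) | k = 7 (all KDQOL visits) |
|---|---|---|
| 3% | 50 × 0.97³ = 45.6 | 50 × 0.97⁷ = 40.4 |
| 5% | 50 × 0.95³ = 42.9 | 50 × 0.95⁷ = 34.9 |
| 10% | 50 × 0.90³ = 36.5 | 50 × 0.90⁷ = 23.9 |

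The seven visits are surgery, day 1, week 1, week 6 and months 6, 12 and 24. They bound the KDQOL loss from above; the planned analysis uses at most three. If missing visits cluster in the same patients, as they do after withdrawal, fewer patients are lost at a given m.

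**3. Precision of the proposed analysis.** With one pair per patient, the 95% CI half-width of each limit is t(0.975, n−1) × √(1/n + 1.96²/(2(n−1))) in SDs of the differences: 0.55 at n = 40, 0.49 at 50 and 0.44 at 60. The flowchart schedules six post-operative PK/PD draws per patient, so the actual model must allow for repeated pairs.

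**The case against.** The strongest reply is that section 8 never assigns these tests to device versus blood. It applies them to evolution over time, and section 6 says only that the two sources will be compared. A reader might infer that the trial would declare the device accurate because p > 0.05; the text does not support that. The simulation shows what would follow if these tests were borrowed for the purpose, and no more.

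A reader might also infer that the six draws would be pooled as independent. Nothing says so, and repeated-measures ANOVA itself allows for within-patient correlation.

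Further, the analysis is described as mainly descriptive, bias and limits of agreement are descriptive quantities, and an unseen SAP may specify them. That is fair as far as it goes: the silence of section 6 alone would not be a finding. But section 8 does more than stay silent. It fixes the tests and attaches the primary hypothesis to KDQOL, so an SAP would have to depart from the protocol to give the primary objective its own primary analysis.

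On KDQOL, collecting seven assessments and testing a few is no contradiction in itself. The fault is that the time points ("at respectively the two and three time-points") are not named. Replacing withdrawn subjects may restore the number of completers, but not the patients whom ANOVA leaves out.

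**Conclusion.** The concern holds in this form: no inferential method named in section 8 addresses the primary objective, and the tests that are named are tied to an endpoint that section 3.3 lists as secondary. That rests on the text alone. That such tests cannot show agreement is a property of the methods; the simulated percentages illustrate it under assumed errors.

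Classical repeated-measures ANOVA conflicts with section 5.4's instruction to use data from withdrawn subjects. For KDQOL at three time points the loss is moderate, to about 46, 43 or 36 of 50 patients at an assumed 3%, 5% or 10% missing per visit. The figures of about 40, 35 or 24 apply only if all seven visits were entered, which section 8 does not plan for KDQOL. Exclusion concerns visits entered in the particular ANOVA, not any visit in the trial; Wilcoxon likewise loses incomplete pairs. The direction of selection, towards uneventful patients, follows from the withdrawal reasons, but the documents do not allow its size to be estimated.

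**What to change.** Amend section 8 as follows.

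1. **Device versus blood.** Make this the analysis of the primary objective. Fit a linear mixed model to the device-minus-blood differences (on the log scale if error grows with concentration), with a patient random effect and visit as a fixed effect, using the six post-operative draws. Report bias and 95% limits of agreement with confidence intervals, the limits being bias ± 1.96 × √(between-patient + within-patient variance). State an acceptance limit in advance, with its justification. Both methods must be on one scale: section 6 does not give the units of the application's output, so specify a calibration step first if these are not concentrations. Add a repeatability SD from consecutive device readings around each draw only if the reading frequency, which the protocol does not give, allows it.
2. **KDQOL and GFR.** Replace Wilcoxon and repeated-measures ANOVA with a mixed model for repeated measures using all collected visits and partial data. State its missing-at-random assumption and discuss it in light of the withdrawal reasons in section 5.4.
3. **Labels.** Name the KDQOL time points of interest and stop describing KDQOL as the primary endpoint hypothesis, so that sections 3.2, 3.3 and 8 agree.

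The cost is redrafting, modest extra analysis and an explicit missing-data assumption. No extra blood samples are needed, and the SPSS package already named can fit these models. A repeatability analysis would also need device readings to be stored around each draw.
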